5.3.4 Duration of effect

For each treatment cycle, duration of treatment effect will be evaluated by the BOTOX treatments groups of the given cycle by assessing the following two variables.

- Time between last BOTOX injection and patient's request for the following injection (re-treatment)
- Time between last BOTOX injection and qualification for retreatment (retreatment with the next injection)

Patients who did not request retreatment for a given cycle will be treated as censored at the time of study exit.

For each cycle, for each treatment group, the Kaplan-Meier survival methodology will be used to estimate the median time to request for re-treatment. Furthermore, the 25th and 75th

percentiles of the time to request for retreatment will be estimated. The associated 95% CIs will also be presented for each treatment group. The proportion of patients requesting retreatment during the study will also be presented.

[figure not shown]
The time to qualification for retreatment will be summarized in a similar manner.

For each patient and BOTOX dose the average time to request for retreatment and the average time to qualification for retreatment will also be derived. Descriptive statistics of these derived values will be presented for each BOTOX dose.

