The adult program was initiated with a phase 2 study (191622-511) that evaluated a single treatment of 200 and 300 U BOTOX versus placebo (N = 59). This study demonstrated clinically and statistically significant improvements with BOTOX compared to placebo in urinary incontinence and urodynamic parameters as well as an improvement in patient-reported health-related quality of life (HRQOL). Two pivotal phase 3 studies were subsequently conducted in spinal cord injury and multiple sclerosis patients who were not adequately managed with anticholinergic therapy (Study 191622-515, N = 416 and Study 191622-516, N = 275). Patients in both studies received 200 U BOTOX, 300 U BOTOX, or placebo administered as intradetrusor injections via cystoscopy. Patients could receive an additional treatment if prespecified retreatment criteria were fulfilled; patients received active treatment with BOTOX for this retreatment (200 or 300 U BOTOX). Patients were to remain in the studies for at least 48 weeks, and those receiving a second treatment were to be followed for at least 12 weeks post-treatment 2. In addition, patients could enter a long-term extension study (191622-094, 3 years duration) in which they could receive multiple treatments of BOTOX (initially of 200 or 300 U BOTOX but subsequently amended to only 200 U). At this time, the study is still ongoing; however data from an interim analysis are available.

Both pivotal phase 3 studies achieved the primary efficacy endpoint of significant reductions in urinary incontinence at week 6; reductions of approximately 20 episodes per week were observed in both BOTOX treatment groups compared to approximately 10 episodes per week in the placebo groups (Cruz et al, 2011; Ginsberg et al, 2012). Efficacy was further supported by achievement of the urodynamic secondary endpoints of a significant increase in maximum cystometric capacity (MCC) and a significant decrease in maximum detrusor pressure during the first involuntary detrusor contraction. Again, no clinically relevant difference was observed between the 200 and 300 U doses. The patient perception of benefit was reflected in the achievement of the HRQOL endpoint in both pivotal studies. The duration of effect of BOTOX was approximately 9 to 10 months.

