## 3. Study Design

This is a multicenter, double-blind, long-term extension study to the preceding study, 191622-120. Patients will roll over directly from the preceding study; the exit visit of study 191622-120 is also the entry visit (day 1) for Study 191622-121 (patients exit Study 191622-120 once they have qualified for retreatment, or at week 48 if they never qualified).

Patients can receive multiple double-blind treatments of 50, 100, or 200 U BOTOX (not to exceed 6 U/kg) in the extension study once they qualify for retreatment (for the first retreatment this qualification may have occurred in the preceding study). The dose received at any given treatment will be determined by the investigator based on the response to the preceding blinded treatment. The investigator can elect to keep the dose the same or increase the dose compared to the preceding treatment (if it is deemed a decrease in dose is warranted, the patient would be exited from the study). The actual dose received remains blinded (unless the patient is requested to exit the study via the IVRS, as described at the end of Section 5.5, or until the interim analysis has been reported as described in Section 7.7). The study medication will be administered via cystoscopy as 20 evenly spaced intradetrusor injections of 0.5 mL each, sparing the trigone.

Following any treatment, patients will have posttreatment follow-up clinic visits at weeks 2, 6, and 12, and then alternating telephone and clinic visits every 6 weeks thereafter until they qualify for further retreatment or exit the study. Request for retreatment can occur at any scheduled clinic or telephone visit, or between scheduled visits. If a request occurs at a scheduled clinic visit, this then becomes a qualification for retreatment visit, otherwise a qualification for retreatment clinic visit should occur within approximately 1 to 2 weeks of request. Patients exit the study once 48 weeks have elapsed since entry on day 1 and at least 12 weeks follow-up since their last study treatment has occurred (exit will therefore be between 48 and 60 weeks since study entry on day 1; the latter being for patients who received retreatment at week 48).

The efficacy measure of key interest is daytime urinary incontinence episodes, and the key timepoint is week 6 after each treatment.

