# 5.5 Method for Assignment to Treatment Groups/Randomization

There will be no randomization in this long-term extension study.

All patients who receive treatment in this study will receive BOTOX. The blinded dose received (50, 100, or 200 U BOTOX, not exceeding 6 U/kg) will be dependent on the assessment of the clinical response (efficacy and safety) to the previous blinded study treatment (which will have been 50, 100, or 200 U BOTOX, not exceeding 6 U/kg). The patient/parent/caregiver will be questioned on their treatment response to establish if, in their opinion, the current treatment response is adequate or if there was little or no treatment benefit and whether they would be willing/want to have a higher dose. They will also be questioned on whether the patient is experiencing side effects. Using this information, the investigator will use his/her own clinical assessment of the patient and apply the following criteria for the retreatment dose request:

- if the benefit/risk balance is evaluated by the investigator to be appropriate at the current dose, then the same dose would be requested
- if the investigator assessed that, although the preceding dose was well tolerated, the
  response received was insufficient and warrants a higher dose, then a dose increase would
  be requested

• if the investigator assessed that there were side effects that would warrant a lower dose, the patient would be exited from the study

Compared to the previous treatment, the investigator therefore has the following options:

- elect to keep the same dose as received at the previous treatment (not to exceed 6 U/kg)
- elect to increase the dose compared to the previous treatment (not to exceed 6 U/kg):
- if the patient received 50 U BOTOX at the previous treatment, they would receive 100 U BOTOX
  - if the patient received 100 U BOTOX at the previous treatment, they would receive 200 U BOTOX
  - if the patient received 200 U BOTOX at the previous treatment, they would remain at 200 U BOTOX (after 2 requests to increase the dose from 200 U the patient will be exited; see below)

At the qualification for retreatment visit the investigator or designee will contact the IVRS/IWRS and indicate the treatment option for the patient. IVRS/IWRS options will be either to remain at the same dose or to increase the dose since patients will be exited from the study if the investigator assessed that a lower dose was warranted (see below).

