#### 5.9 Treatment Administration

# 5.9.1 Day of Treatment Criteria

Treatment will be administered within 4 weeks of qualification for retreatment (see Section 5.10.1 for qualification for retreatment criteria), but no later than 48 weeks since study enrollment on day 1 of this study. The following "day of treatment criteria" must be fulfilled prior to each administration of study medication:

- patient does not have a UTI, in the opinion of the investigator (taking into account patient symptoms, presence of significant leukocyturia at screening (e.g. ≥ 30 WBC/HPF), urine culture results, need for antibiotic treatment,etc)
- appropriate prophylactic antibiotics have been initiated (see Section 5.9.2)
- antiplatelet or anticoagulant therapy or medications with anticoagulative effects have been discontinued at least 3 days prior to treatment
- negative urine pregnancy result (for postmenarche females)
- investigator continues to deem treatment is appropriate and no condition or situation exists which, in the investigators opinion, puts the patient at significant risk from receiving retreatment

Note: If a patient does not fulfill the "day of treatment criteria", they would still be considered qualified for retreatment (ie, qualification for retreatment or any associated procedures are not to be repeated). The treatment administration visit would be rescheduled for as soon as possible (if applicable), and the day of treatment criteria would need to be fulfilled prior to treatment administration.

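### The per-patient average times to retreatment by dose ignore censoring, so they understate duration and can make higher doses look shorter-acting

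*SAP*

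**What the plan says.** SAP 5.3.4 plans two kinds of duration summary. The first is Kaplan-Meier by cycle and treatment group (median and quartiles with 95% CIs), under the rule "Patients who did not request retreatment for a given cycle will be treated as censored at the time of study exit". The second is "For each patient and BOTOX dose the average time to request for retreatment", and the same for qualification, with descriptive statistics for each dose. SAP 2.3 defines descriptive statistics for continuous variables as n, mean, SD, median, quartiles and extremes, so no survival estimator is involved. No rule is given for intervals without a request.

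The design features that matter are in the protocol:

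- The dose preceding the first retreatment is already an active one ("which will have been 50, 100, or 200 U BOTOX, not exceeding 6 U/kg", Protocol 5.5), so first-cycle intervals exist at all three doses.
- "The investigator can elect to keep the dose the same or increase the dose compared to the preceding treatment" (Protocol 3). An increase is requested when the "response received was insufficient and warrants a higher dose" (Protocol 5.5).
- Retreatment is given "no later than 48 weeks since study enrollment on day 1 of this study" (Protocol 5.9.1), and "exit will therefore be between 48 and 60 weeks since study entry on day 1" (Protocol 3).
- Patients leave Study 191622-120 when they qualify for retreatment, or at week 48 (Protocol 3).

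**The concern.** An arithmetic average has no way to use the information that an interval lasted at least a given time. If open intervals are dropped, the long ones are removed selectively. If they enter at the exit time, they are cut short. Both push the average down.

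The push is not equal across doses. Intervals after a retreatment are observed for much less time than first-cycle intervals, and with same-or-up dosing any escalation moves these short-window intervals towards 200 U. A dose trend can then appear when there is none, or a real gain can be hidden.

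Duration of effect is a named efficacy measure (Protocol 6.1.4). These averages are the only duration summary in the SAP that combines cycles by dose, so they are likely to be read as duration by dose. The SAP sees the same difficulty for adverse events: section 6.2 adds a summary limited to the first 84 days of each cycle, so that doses are compared over equal time. The duration averages have no such safeguard.

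**Working it through.** The plan gives no figure for this summary, so there is nothing to reproduce.

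**1. Observation windows (from the documents).** A first-cycle interval can be followed for 48 weeks in Study 191622-120 plus 48 weeks here, 96 in all. For a retreatment given *t* weeks after entry (0 ≤ *t* ≤ 48), exit is at max(48, *t* + 12), so follow-up is max(48 − *t*, 12): 48 weeks at *t* = 0, 24 at *t* = 24, and 12 from *t* = 36 onward.

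**2. What the window alone does.** The documents give no paediatric duration. I assume time to request T = 12 weeks + Weibull with shape 1.3, and an overall median of 39 weeks, which is the lower end of the protocol's adult statement, "The duration of effect of BOTOX was approximately 9 to 10 months" (Protocol 1).

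- Scale = (39 − 12)/(ln 2)^(1/1.3) = 35.8
- True mean = 12 + 35.8 × Γ(1 + 1/1.3) = 45.1 weeks
- Proportion still open at window C: S(C) = exp(−((C − 12)/35.8)^1.3)
- Mean with exit as event: E[min(T, C)] = ∫₀^C S(u) du
- Mean of completed intervals: (E[min(T, C)] − C·S(C))/(1 − S(C))

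| Window C (weeks) | Open, S(C) | Completed only | Exit as event |
|---|---|---|---|
| 96 | 0.05 | 41.5 | 44.1 |
| 48 | 0.37 | 29.5 | 36.3 |
| 24 | 0.79 | 18.6 | 22.8 |

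For C = 48: (36.27 − 48 × 0.365)/(1 − 0.365) = 29.5. The same true distribution, with mean 45.1, gives very different averages according to the window.

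**3. What the mix of windows does by dose.** I simulated 200,000 patients per scenario under the documented entry, retreatment and exit rules. Assumed: starts at 50/100/200 U with probability 1/3 each, 3 weeks from request to injection, identical true durations at every dose, successive intervals independent, and escalation by one level with fixed probability at each retreatment. Median 39 weeks:

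| Escalation 0.5 | 50 U | 200 U |
|---|---|---|
| Completed only | 40.5 | 36.8 |
| Exit as event | 41.4 | 32.6 |
| Pooled Kaplan-Meier median | 39.0 | 38.9 |
| Intervals censored | 24% | 48% |

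Without escalation the averages are about 39.5 (completed) and 37.6 (exit as event) at every dose. That is 45.1 − 39.5 = 5.6 and 45.1 − 37.6 = 7.5 weeks below the true mean, with a dose gap of about 0.

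Gap, 200 U minus 50 U, for escalation 0.2 to 0.5:

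| True median (weeks) | Completed only | Exit as event |
|---|---|---|
| 39 | −1.7 to −3.7 | −4.4 to −8.8 |
| 26 | −1.0 to −2.1 | −2.7 to −5.1 |
| 20 | −0.4 to −0.8 | −1.6 to −2.8 |

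**4. Size against sampling error.** At N = 78 to 100 (the SAP's and the protocol's expected enrolment) and median 39, the SE of the difference is 4.5 to 5.3 weeks (completed) or 4.1 to 4.8 (exit as event). The largest completed-only gap is 3.7/4.5 = 0.8 SE. With exit as event the range is about 4.4/4.8 = 0.9 to 8.8/4.1 = 2.1 SE.

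**5. Sensitivity, median 39, escalation 0.2 to 0.5.**

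- Request-to-injection gap of 0 to 4 weeks: −1.6 to −3.8 (completed), −4.4 to −9.3 (exit as event).
- Weibull shape 1.0 to 2.0: −1.2 to −3.8 and −3.9 to −9.3.
- Starts 10/10/80%: about −0.7 to −1.5 and −2.2 to −4.8. Starts 60/30/10%: about −3.5 to −7 and −7.8 to −13.4.

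**6. A different model.** With lognormal times, within-patient correlation 0.5 and medians of 20, 30 or 40 weeks, the averages were low in all 18 scenarios. When each dose step truly lasted 10% longer (median 30, escalation 0.5), exit-as-event means still fell with dose: 32.2 weeks at 50 U against 29.2 at 200 U. Completed-only means kept the right order but shrank the gap. At median 40, true means of 46.4 and 54.8 appeared as 42.1 and 44.6.

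**The case against.** The strongest reply is that an interval with no request has no time to request, so the natural reading is completed intervals only. Entering exit as a request would contradict the censoring rule in the same section. On that reading, with equal starting groups, the artefact is below one standard error. The study tests no hypotheses, the protocol's own duration analysis is Kaplan-Meier by cycle and dose, and no comparison between doses is planned on the averages. This stands as a limit on severity. The larger exit-as-event figures should be read as the less likely case. The completed-only reading still understates duration and can still produce the trend.

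The figures are also not bounds. The starting-dose split matters a great deal, and the comparison with the SE was made only for equal starts. Early discontinuation and the exit after two increase requests at 200 U were not modelled. This stands too: the direction is firm, the exact weeks are not.

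Kaplan-Meier is not perfect either. With correlated intervals within a patient, the pooled 200 U minus 50 U gap is about −0.7 to −1.6 weeks even with random escalation. In the lognormal model (median 30, escalation 0.5) the cycle 3 medians are 22.6 to 23.1 weeks against true values of 26.0 to 27.0, though not falsely ordered by dose. Pooling also gives more weight to patients who are retreated often. These points qualify the replacement, but its error is far smaller than that of the averages.

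**Conclusion.** The concern holds. As specified, the per-patient averages understate duration under either reading of the SAP, and the understatement grows with dose once patients escalate. With equal true durations at a median of 39 weeks, equal starts and 20% to 50% escalation, the spurious 200 U minus 50 U difference is −1.7 to −3.7 weeks (completed only) or −4.4 to −8.8 weeks (exit as event). It is smaller with shorter durations or mostly 200 U starts, larger with mostly 50 U starts, and absent without escalation. A large true gain with dose would be compressed rather than reversed.

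Durations, escalation rates and starting split are all assumptions. The mechanism needs only the documented windows, same-or-up dosing and some escalation. The effect is confined to one untested supplementary table, so this is a moderate correction that should be made and not a threat to the main duration analysis.

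**What to change.** Delete the per-patient averages from SAP 5.3.4. If a summary by dose across cycles is wanted, replace them with a Kaplan-Meier estimate per dose pooled over cycles, for both request and qualification. Report the median, quartiles, number of intervals and number censored, with a bootstrap confidence interval that resamples patients.

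State beside the table that escalation follows insufficient response, so differences between doses still reflect patient selection. In a check with escalation concentrated in short responders (lognormal frailty SD 0.4, average rate 0.5, median 39), pooled Kaplan-Meier gave 38.2 weeks at 50 U against 36.8 at 200 U, compared with 39.8 against 33.6 for exit as event. Pooling removes most of the artefact but not the selection.

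If the averages are kept all the same, the minimum is to say that only completed intervals enter, give the number of open intervals by dose, and label the table as not comparable across doses. This discloses the bias but does not remove it.

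The cost is SAP wording and at most one replacement table, with no new data. The drawback is that upper quantiles may not be estimable at some doses.

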5.3.5 Modified Treatment Benefit Scale (TBS)

The modified Treatment Benefit Scale (TBS) is single-item scale completed for each cycle at weeks 6 and 12 post-treatment, and at the qualification for retreatment visit if the patient qualifies for re-treatment.

A patient is considered to have a positive treatment response if she/he has responded to the TBS question as either "greatly improved" or "improved". For each treatment cycle, the numbers and proportions of patients with a positive treatment response will be summarized by visit (week 6 and 12) and treatment group.

6. Safety Analyses

Safety information includes treatment exposure, adverse events, laboratory assessments, vital signs and bladder and kidney ultrasound assessment.

6.1.2 Administration of Study Treatment(s)

For the BOTOX injections, a patient listing will be produced. The listing will present, for each patient, the time and date of all the injections, the number of injection sites and volume injected.

6.2 Adverse Events

Adverse events (AEs) will be coded by system organ class and preferred term using the Medical Dictionary for Regulatory Activities (MedDRA).

Pre-treatment AEs are AEs that have start date on or after the signing of consent form and prior to the first BOTOX injection.

An AE will be considered a cycle 1 treatment-emergent adverse event (TEAE) if it fulfills one of the conditions below:

• the start date of the AE is on or after the 1st BOTOX injection and prior to the date of the 2nd BOTOX injection

• the AE started before the 1st BOTOX injection and increased in severity or became serious during the cycle (from date of 1st BOTOX injection to the day before the 2nd injection).

For subsequent cycles (cycle's number > 1) an AE is considered a TEAE in the current cycle if it fulfills one of the conditions listed below.

- the AE start date is within the cycle i.e., it is on or after the date of the cycle injection and prior to the date of the next injection
- the AE has increased in severity or became serious during the current cycle

The incidences of TEAEs will be summarized by BOTOX treatment cycle.

The number and percentage of patients reporting TEAE in each treatment group will be tabulated by descending percentage in any group, by system organ class and preferred term, and further categorized by severity and causal relationship to the study drug and study drug injection procedure. If more than 1 AE is coded to the same patient, the patient will be counted only once for that preferred term using the greatest severity for the summarization by severity and causal relationship.

The number and percentage of patients who have treatment-emergent serious adverse events (TESAE) will be summarized by system organ class, preferred term and treatment group. Similar summary will be presented for patients with TEAE leading to discontinuation from the study. In addition, separate patient listings will be generated for deaths, SAEs, and TEAEs leading to study discontinuation.

In addition, the incidence of TEAEs, SAEs, study drug/study injection procedure related TEAEs, deaths and TEAEs leading to study discontinuation will be reported for the overall study period.

All the summaries discussed above will be based on all AEs observed during the entire cycle. Since the design of this study allows patients to request/receive retreatment from week 12 (day 84) onward, an additional summary showing the number and percentage of patients with TEAEs by preferred term and treatment group in descending order of incidence will be presented for the TEAE observed prior to or on day 84 after each injection cycle. This will allow for a comparison across dose groups for the same duration of time (ie, since patients can request retreatment from week 12 onwards, patients remain in a cycle for varying time periods). Therefore this analysis provides a more direct comparison across dose groups.

In addition, the number and percentage of patients who have a treatment-emergent UTI during the first 2 weeks (14 days), the first 12 weeks (84 days), and during the overall treatment cycle will be presented by the treatment received in each treatment cycle.

The number of UTI events per patient year will be summarized for the six month prior to screening and for each BOTOX treatment cycle. The number of UTI events per patient year, for the BOTOX treatment cycle, is defined as follows: (The sum of all the patients UTI events)/ (The sum of all the patients duration in years during the BOTOX treatment cycle). The number of UTI events per patient year for the 6-months prior to screening is similarly defined. All patients will be included in these analyses irrespective of whether they experienced a UTI or not.

